2.4 Correlative Studies Background

2.4.1 Pharmacokinetic Studies

While the pharmacokinetic data of weekly AT13387 and the combination of dabrafenib and trametinib are known, PK data of the triple combination will be investigated as part of the Phase I portion of this study. Clinically observed toxicities will be correlated with the possibility of delayed clearance of the individual agents.

The PK sampling regimen for this study is based on the following observations; steady state for trametinib was reached by approximately Day 15 and the C_{max} and AUC for dabrafenib at the RP2D are about 40% lower on Day 15 versus Day 8. In addition, accumulation of trametinib was observed in the combination study of trametinib and dabrafenib.

Measurement of drug levels of AT13387, dabrafenib, and trametinib will be performed on Cycle 1 day 15 of three-drug treatment (pre-, 1, 2, 4, 6, and 8 hours after dosing), and Cycle 1 day 16 (24 hours after AT13387 day 15 dosing). Samples for trough level PK analysis will then be planned for each patient on day 1 of cycles 2, 4, 8, and 12.

2.4.2 Biomarkers of Drug Effect

[figure not shown]

Figure 2.3.3: Effect of AT13387 on HSP90 clients in melanoma xenografts. Mice bearing (A) A375, (B) A2058, or (C) RPMI-7951, SK-MEL-5, or WM266.4 tumor xenografts were treated with single doses of 70 mg/kg AT13387.

Although we do not yet know which HSP90 client proteins must be degraded in order for long term anti-tumor responses to be seen to the BRAF/MEK/HSP90 inhibitor combination, preliminary studies from our group and others suggests that the PI3K/AKT/mTOR pathway may be critical for the short-term adaptive responses to BRAF inhibition and that prolonged inhibition of the Raf/MEK/ERK/CDK4/Cyclin D1 pathway is required for durable anti-tumor response. Levels of HSP90 client proteins, HSP chaperones and other proteins involved in adaptive signaling responses will be measured using LC-MRM from FNAs taken from accessible melanoma lesions before therapy initiation and after 7-10 days of BRAF/MEK/HSP90 treatment.

Additionally, biopsy specimens will be evaluated by Reverse Phase Protein Array (RPPA) at RPPA Core Facility, [name] Anderson Cancer Center (Texas, USA). Primary targets of interest for analysis of AT13387 effect on relevant HSP90 client proteins in tumor biopsy tissue will be evaluated. Frozen biopsy specimens obtained during collection will be sent for analysis of relevant proteins, protein post-translational modifications (phosphorylation and other modifications) and effects on relevant signaling pathways.

2.4.3 Blood Based BRAF Assay

Our group has developed a blood-based assay that can measure circulating BRAF levels in patients with BRAF mutant melanoma. (Panka *et al.*, 2010; Panka *et al.*, 2014) Our data shows that the BRAF level is reduced in patients treated with BRAF-directed therapy (both single-agent vemurafenib and the combination of DT) and, in some patients, increases in advanced of clinical or radiographic progression by 40-60 days. (Panka *et al.*, 2014) As this assay remains under clinical development, we plan to measure serial values (pre-treatment and at the beginning of each cycle) to further interrogate the utility of this assay. All samples will be initially processed in the Translational Research Laboratory at MGH and then subsequently assayed at the BIDMC.

3. PATIENT SELECTION

3.1 Eligibility Criteria

3.1.1 Patients must have histologically confirmed, BRAF-mutant (V600E/K) solid tumor (molecularly confirmed using Cobas assay or a comparable FDA-approved assay) that is metastatic or unresectable, have received and tolerated prior BRAF or BRAF and MEK inhibitor (BRAF targeted) therapy at full dose or not previously received BRAF targeted therapy, and for which standard curative measures do not exist or are no longer effective.

- If test at CLIA-certified lab used a non-FDA approved method, information about the assay must be provided. (FDA approved tests for BRAF V600 mutations in melanoma include: THxID BRAF Detection Kit and Cobas 4800 BRAF V600 Mutation Test).

3.1.2 Patients must have measurable disease, defined as at least one lesion that can be accurately measured in at least one dimension (longest diameter to be recorded for non-nodal lesions and short axis for nodal lesions) as ≥ 20 mm with conventional techniques or as ≥ 10 mm with spiral CT scan, MRI, or calipers by clinical exam. See Section 11 for the evaluation of measurable disease.

3.1.3 Prior therapy is allowed. Patients may have received any number of prior lines of therapy, including treatment with a BRAF and/or MEK inhibitor.

3.1.4 All prior anti-cancer treatment-related toxicities must be less than or equal to Grade 1 according to the Common Terminology Criteria for Adverse Events version 5 (CTCAE version 5.0; NCI,2017) at the time of enrollment. **A notable exception** are endocrinopathies caused by immune checkpoint inhibitors that are appropriately treated with medical management (e.g. hormone replacement therapy, anti-diabetic agents)

3.1.5 Age ≥ 18 years. Because no dosing or adverse event data are currently available on the use of AT13387 in combination with dabrafenib and trametinib in patients <18 years of age, children are excluded from this study, but will be eligible for future pediatric trials.

3.1.6 ECOG performance status ≤ 1 (Karnofsky $\geq 70\%$, see Appendix A).

3.1.7 Life expectancy of greater than 3 months.

3.1.8 Patients must have normal organ and marrow function as defined below:

- leukocytes	$\geq 3,000/\text{mcL}$
- absolute neutrophil count	$\geq 1,200/\text{mcL}$
- hemoglobin	$\geq 9 \text{ g/dL}$ (patients may be transfused to this level)
- platelets	$\geq 100,000/\text{mcL}$
- total bilirubin	$< 1.5 \times$ institutional upper limit of normal OR $> 1.5 \times$ institutional upper limit of normal allowed if direct bilirubin is within normal range.
- AST(SGOT)/ALT(SGPT)	$\leq 2.5 \times$ institutional upper limit of normal
- PT/INR and PTT	$\leq 1.3 \times \text{ULN}$
- Serum creatinine	$\leq 1.5 \text{ mg/dL}$ OR $\geq 50 \text{ mL/min}/1.73 \text{ m}^2$
- creatinine clearance	> 3 and $< 5.5 \text{ mEq/L}$
- Potassium	> 1.2 and $< 2.5 \text{ mEq/L}$
- Magnesium	\geq institutional lower limit of normal (LLN) by ECHO
- Left ventricular ejection fraction	

3.1.9 The effects of AT13387, dabrafenib, and trametinib on the developing human fetus are unknown. For this reason, women of child-bearing potential must have a *negative serum pregnancy test within 14 days prior to randomization and agree to use effective contraception* (barrier method of birth control, or abstinence; hormonal contraception is not allowed due to drug-drug interactions which can render hormonal contraceptives ineffective) *from 14 days prior to randomization*, throughout the treatment period, and for 4 months after the last dose of study treatment. Should a woman become pregnant or suspect she is pregnant while she is participating in this study, she should inform her treating physician immediately.

Based on studies in animals, it is also known that dabrafenib may cause damage to the tissue that makes sperm. This may cause sperm to be abnormal in shape and size and could lead to infertility, which may be irreversible.

Safety and efficacy of the combination of dabrafenib and trametinib in pediatric populations have not been investigated. Dabrafenib or trametinib-dabrafenib combination should not be administered to pediatric populations outside clinical trials.

3.1.10 Therapeutic level dosing of warfarin can be used with close monitoring of PT/INR by the site. Exposure may be decreased due to enzyme induction when on treatment, thus warfarin dosing may need to be adjusted based upon PT/INR. Consequently, when discontinuing dabrafenib, warfarin exposure may be increased and thus close monitoring via PT/INR and warfarin dose adjustments must be made as clinically appropriate. Prophylactic low dose warfarin may be given to maintain central catheter patency.

3.1.11 Ability to understand and the willingness to sign a written informed consent document.

3.1.12 Able to swallow and retain oral medication, *and must not have any clinically significant gastrointestinal abnormalities that may alter absorption such as malabsorption syndrome or major resection of the stomach or bowels*

3.2 Exclusion Criteria

3.2.1 Patients who received prior systemic anti-cancer therapy (chemotherapy with delayed toxicity, extensive radiation therapy, immunotherapy, biologic therapy, or vaccine therapy) within the last 3 weeks prior to Day 1 of Cycle 1. Patients are permitted to be on dabrafenib and trametinib standard of care at start of therapy without wash-out period prior to Day 1 of Cycle 1. Dosing will change to protocol determined dose levels on Day 1 of Cycle 1.

3.2.2 Patients must not have received prior HSP90 inhibitor therapy.

3.2.3 Patients who are receiving any other investigational agents. Patients who have taken an investigational drug within 28 days or 5 half-lives (minimum 14 days), whichever is shorter, prior to randomization.

- 3.2.4 Patients with history of RAS mutation positive tumors regardless of interval from current study. However, patients may have concurrent BRAFV600 and RAS mutations in the tumor to be treated with protocol therapy.
- 3.2.5 Patients must have no clinical evidence of leptomeningeal or brain metastasis causing spinal cord compression that are symptomatic or untreated or not stable for ≥ 4 weeks (must be documented by imaging) or requiring corticosteroids. Subjects on a stable dose of corticosteroids >1 month or who have been off of corticosteroids for at least 2 weeks can be enrolled with approval of the CTEP medical monitor. Subjects must also be off of enzyme-inducing anticonvulsants for >4 weeks.
- 3.2.6 History of known immediate or delayed hypersensitivity reactions attributed to compounds of similar chemical or biologic composition to AT13387, dabrafenib, or trametinib, or excipients or to dimethyl sulfoxide (DMSO).
- 3.2.7 Uncontrolled intercurrent illness including, but not limited to, ongoing or active serious infection, symptomatic congestive heart failure, unstable angina pectoris, cardiac arrhythmia, uncontrolled diabetes, or psychiatric illness/social situations that would limit compliance with study requirements.
- 3.2.8 Pregnant women are excluded from this study because AT13387, dabrafenib, and trametinib may have teratogenic or abortifacient effects. Because there is an unknown but potential risk for adverse events in nursing infants secondary to treatment of the mother with the study drugs, breastfeeding should be discontinued *prior to* the mother being treated with the study drugs.
- 3.2.9 Patients known to be HIV-positive patients and on combination antiretroviral therapy are ineligible because of the potential for pharmacokinetic interactions with the study drugs. In addition, these patients are at increased risk of lethal infections when treated with marrow-suppressive therapy. Appropriate studies will be undertaken in patients receiving combination antiretroviral therapy when indicated.
- 3.2.10 History of another malignancy other than the study indication under this trial within 5 years of study enrollment. Does not apply to subjects who underwent successful definitive resection of basal or squamous cell carcinoma of the skin, superficial bladder cancer, in situ cervical cancer, in situ breast cancer, or other in situ cancers.

Exception: Patients with history of RAS mutation-positive tumors are not eligible regardless of interval from the current study. Prospective RAS testing is not required. However, if the results of previous RAS testing are known, they must be used in assessing eligibility.

- 3.2.11 History of interstitial lung disease or pneumonitis.
- 3.2.12 History or current evidence/risk of retinal vein occlusion (RVO) or retinal pigment epithelial detachment (RPED):

- History of RVO or RPED, or predisposing factors to RVO or RPED (e.g., uncontrolled glaucoma or ocular hypertension, uncontrolled systemic disease such as hypertension, diabetes mellitus, or history of hyperviscosity or hypercoagulability syndromes).
- Visible retinal pathology as assessed by ophthalmic exam that is considered a risk factor for RVO or RPED such as evidence of new optic disc cupping, evidence of new visual field defects, and intraocular pressure >21 mm Hg.

3.2.13 History or evidence of cardiovascular risk including any of the following:

- An average of the three most recent QT intervals corrected for heart rate using the Bazett's formula QTcB ≥ 460 msec.
- History or evidence of current clinically significant uncontrolled arrhythmias (exception: patients with controlled atrial fibrillation for >30 days prior to randomization are eligible).
- History of acute coronary syndromes (including myocardial infarction and unstable angina), coronary angioplasty, or stenting within 6 months prior to randomization.
- History or evidence of current \geq Class II congestive heart failure as defined by the New York Heart Association (NYHA) functional classification system
- Treatment-refractory hypertension defined as a blood pressure of systolic >140 mmHg and/or diastolic >90 mmHg which cannot be controlled by anti-hypertensive therapy.
- Abnormal cardiac valve morphology (\geq grade 2) documented by echocardiogram (subjects with grade 1 abnormalities [i.e., mild regurgitation/stenosis] can be entered on study). Subjects with moderate valvular thickening should not be entered on study.
- Prior placement of an implantable defibrillator
- History of or identification on screening imaging of intracardiac metastases

3.2.14 No known active infection with Hepatitis B Virus (HBV), or Hepatitis C Virus (HCV). Patients with chronic or cleared HBV infection and HCV infection are eligible.

3.2.15 Current use of a prohibited medication. The following medications or non-drug therapies are prohibited (Please refer to Appendix F for complete list):

- Other anti-cancer therapy while on study treatment. (note: megestrol [Megace] if used as an appetite stimulant is allowed).
- Concurrent treatment with bisphosphonates is permitted; however, treatment must be initiated prior to the first dose of study therapy. Prophylactic use of bisphosphonates in patients without bone disease is not permitted, except for the treatment of osteoporosis.
- Because the composition, PK, and metabolism of many herbal supplements are unknown, the concurrent use of all herbal supplements is prohibited during the study (including, but not limited to, St. John's wort, kava, ephedra [ma huang], ginkgo biloba, dehydroepiandrosterone [DHEA], yohimbe, saw palmetto, or ginseng).

Current use of a prohibited medication. Patients receiving any medications or substances that are strong inhibitors or inducers of CYP3A or CYP2C8 are ineligible. Current use of, or intended ongoing treatment with: herbal remedies (e.g., St. John's wort), or strong inhibitors or inducers of P-glycoprotein (Pgp) or breast cancer resistance protein 1 (Bcrp1) should also be excluded. Below are a few examples of the agents.

PROHIBITED – strong inducers of CYP3A or CYP2C8, since concentrations of dabrafenib may be decreased	
Class/Therapeutic Area	Drugs/Agents
Antibiotics	Rifamycin class agents (e.g., rifampin, rifabutin, rifapentine),
Anticonvulsant	Carbamazepine, oxcarbazepine phenobarbital, phenytoin, s-mephentyoin
Miscellaneous	bosentan, St. John's wort

PROHIBITED – Strong inhibitors of CYP3A, or CYP2C8 since concentrations of dabrafenib may be increased	
Class/Therapeutic Area	Drugs/Agents
Antibiotics	Clarithromycin, telithromycin, troleandomycin
Antidepressant	Nefazodone
Antifungals	Itraconazole, ketoconazole, posaconazole, voriconazole
Hyperlipidemia	Gemfibrozil
Antiretroviral	ritonavir, saquinavir, atazanavir
Miscellaneous	Conivaptan

Because the lists of these agents are constantly changing, it is important to regularly consult a frequently-updated list such as <http://medicine.iupui.edu/clinpharm/ddis/main-table/>; medical reference texts such as the Physicians' Desk Reference may also provide this information. As part of the enrollment/informed consent procedures, the patient will be counseled on the risk of interactions with other agents, and what to do if new medications need to be prescribed or if the patient is considering a new over-the-counter medicine or herbal product. Appendix C is a patient information sheet that can be used for this specific protocol and presented to the patient.

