Hypersensitivity: There has been a single report of hypersensitivity (blisters) to dabrafenib, occurring on the same day as the 1st dose of study drug as well as upon rechallenge (IB, 2013). The subject recovered after interruption and then discontinuation of dabrafenib. Grade 1 AEs of blisters on limbs (4 subjects) and drug hypersensitivity (rash, 1 subject) have been reported in previous studies with dabrafenib. However, the precise etiology of these events is unclear.

Hypersensitivity to trametinib was reported by one subject 7 days after starting trametinib who experienced fever, asthenia, visual disturbance, and symptoms suggestive of a hypersensitivity reaction described by the investigator as "vascularity." This subject also developed LFT elevations, lower limb nodules that by biopsy showed "dermo-

hypodermatitis with plasmocyte and lymphocyte infiltrate.” The subject recovered after discontinuation of trametinib.

Hemorrhages (dabrafenib-trametinib combination): Hemorrhage is an AE identified with the dabrafenib-trametinib combination therapy. Hemorrhages, including major hemorrhages defined as symptomatic bleeding in a critical area or organ, can occur with dabrafenib plus trametinib combination therapy (FDA label). In study BRF113220, treatment with dabrafenib in combination with trametinib resulted in an increased incidence and severity of any hemorrhagic event: 16% (9/55) of patients treated with trametinib in combination with dabrafenib compared with 2% (1/53) of patients treated with dabrafenib as a single agent. The major hemorrhagic events of intracranial or gastric hemorrhage occurred in 5% (3/55) of patients treated with trametinib in combination with dabrafenib compared with none of the 53 patients treated with dabrafenib as a single agent. Intracranial hemorrhage was fatal in two (4%) patients receiving the combination of trametinib and dabrafenib.

Glucose-6-phosphate dehydrogenase (G6PD) deficiency (dabrafenib or dabrafenib-trametinib combination): Dabrafenib, which contains a sulfonamide moiety, confers a potential risk of hemolytic anemia in patients with G6PD deficiency; these patients should be closely observed for signs of hemolytic anemia.

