4.4 Registration Process For Other Participating Institutions

External sites will only be registering patients to the protocol with Theradex via IWRS and not with DF/HCC. Sites will follow any site-specific processes as applicable.

The registration procedures are as follows:

- Obtain written informed consent from the participant prior to the performance of any protocol specific procedures or assessments.
- Verify all protocol eligibility criteria. **To be eligible for registration to the protocol, the participant must meet all inclusion and exclusion criterion as described in the protocol.**

Reminder: Confirm eligibility for ancillary studies at the same time as eligibility for the treatment protocol. Registration to both treatment and ancillary protocols will not be completed if eligibility requirements are not met for all studies.

- Designee will register patient with Theradex via IWRS.

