 - a. Informed Consent can be obtained 28 days prior to the first dose
 - b. If within 3 days of screening, this assessment does not need to be repeated on Day 1 of the first dose
 - c. Serum Pregnancy test (Woman of childbearing potential only) done within 72 hours of first dose.
 - d. Dermatological Examination done at screening and then every 8 weeks (2 cycles)
 - e. Ophthalmological examination is done at screening, week 4, and annually; additional ophthalmic exams will be performed only as symptomatically warranted
 - f. Triple EKG will be collected at intervals according to the treating institution's standards prior to each AT13387 infusion
 - g. sodium, potassium, carbon dioxide/bicarbonate, BUN creatinine, glucose, calcium, magnesium, phosphorus, AST, ALT, total Bilirubin, Alkaline phosphatase, total protein and albumin, LDH, hematology includes CBC with differentials and platelets
 - h. Echo/MUGA is done at screening, week 4, week 12, week 24 and every 12 weeks thereafter.
 - i. Includes PT, PT-INR, PTT, repeated as indicated
 - j. Tumor measurements and radiological exam done every other (odd) cycle within 7 days of day 1 treatment. Documentation (radiologic) must be provided for patients removed from the study for progressive disease. Brain CT/MRI is required at baseline for patients with melanoma.
 - k. PK for phase 1: Cycle 1 Days 1 and 15; pre, 1, 2, 4, 6, 8, 24 hour post dose, Day 1 in Cycles 2, 4, 8, and 12.
 - l. In patients with biopsiable disease; pre treatment, Cycle 1 Day 8 (+/- 3 days), at disease progression (if possible)
 - m. Blood BRAF analysis performed C1 D1, C1 D15, at the beginning of each subsequent cycle and at disease progression.
 - n. AE assessment starting from the day 1 of dosing throughout the study
 - o. After 28 day follow up visit, patient is followed for survival only. Survival status is to be collected every 6 months (+/- 2 weeks) for up to 2 years and can be completed by phone. Patients removed from study treatment for any reason other than progressive disease will be followed until disease progression or death, whichever occurs first.
 - p. After cycle 6, hematology/clinical chemistry are collected on Day 8 and Day 15 at the investigator's discretion.

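### As worded, exclusion criterion 3.2.5 does not bar a symptomatic, untreated or unstable brain metastasis unless it also compresses the spinal cord; this looks like a drafting error and should be corrected.

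*Combined protocol and SAP*

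**What the plan says.** Section 3.2.5 (Exclusion Criteria) has three sentences.

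- The first requires "no clinical evidence of leptomeningeal or brain metastasis causing spinal cord compression that are symptomatic or untreated or not stable" for at least 4 weeks, and continues "must be documented by imaging) or requiring corticosteroids".
- The second makes an allowance that needs the CTEP medical monitor's approval: "Subjects on a stable dose of corticosteroids >1 month or who have been off of corticosteroids for at least 2 weeks can be enrolled".
- The third adds a washout: "Subjects must also be off of enzyme-inducing anticonvulsants for >4 weeks".

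A footnote to the study calendar (section 10) adds "Brain CT/MRI is required at baseline for patients with melanoma". It does not say what follows for eligibility if the scan is positive. Section 3.1.1 admits any BRAF V600E/K solid tumor, so the footnote does not cover every eligible tumor type.

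On how criteria are applied, section 4.4, for institutions outside DF/HCC, says "the participant must meet all inclusion and exclusion criterion as described in the protocol". Section 4.1, for DF/HCC institutions, has an investigator confirm eligibility and a study team member complete a protocol-specific checklist. That checklist is not in the documents.

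**The concern.** A brain metastasis does not ordinarily compress the spinal cord. If the cord-compression phrase qualifies it, the exclusion misses the patients it appears to be written for, namely those with active disease in the brain. An eligibility rule is operative text: sites are told to apply the criteria as they stand, and an auditor will compare enrolled patients with them. One site could follow the presumable intent and another the wording, and each could defend its decision.

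The safety background gives a reason to want this criterion to be clear. Section 2.2.2.4, on the dabrafenib-trametinib combination, reports: "Intracranial hemorrhage was fatal in two (4%) patients receiving the combination of trametinib and dabrafenib". Who may enter with brain disease should not turn on how a reader parses one clause.

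**Working it through.** No arithmetic applies. The check sets the possible readings of the sentence side by side, then looks for other text that would close the gap.

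**1. Readings of the first sentence of 3.2.5**

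| Reading | Brain metastasis without cord compression, symptomatic or untreated | Leptomeningeal disease without cord compression, symptomatic or untreated |
|---|---|---|
| A. The cord-compression phrase limits both nouns | Not excluded | Not excluded |
| B. The phrase limits brain metastasis only | Not excluded | Excluded |
| C. Three separate items: leptomeningeal, brain, cord compression | Excluded | Excluded |

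The printed text supports A or B. Reading C needs a comma or a connector before the cord-compression phrase, and neither is there. The result for brain metastases is the same under A and B.

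**2. Signs of intent.** The verb that introduces the conditions is plural although the noun before it is singular, which suggests a list that has lost a word. Imaging-documented stability, corticosteroid dependence and an anticonvulsant washout are natural conditions for brain and leptomeningeal disease in general. They have little purpose if confined to a brain lesion that compresses the cord. Both signs point to C as the intent.

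**3. Other text that might close the gap**

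- *Second sentence of 3.2.5:* an allowance tied to corticosteroid use, not a separate bar on brain metastases.
- *Third sentence of 3.2.5, and the strong CYP3A inducers prohibited in 3.2.15:* these catch only patients taking such drugs.
- *ECOG status of at most 1 (3.1.6), life expectancy above 3 months (3.1.7), uncontrolled intercurrent illness (3.2.7):* these keep out some of the sickest patients, but none names brain metastases and none is a general bar.
- *Calendar footnote:* a scan for melanoma only, with no stated consequence for eligibility.

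No other criterion in sections 3.1 or 3.2 addresses brain metastases.

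**4. A second inconsistency in the same item.** The first sentence excludes on the need for corticosteroids. The second allows patients on a stable dose for more than 1 month to enter with approval. The second may be meant as an exception to the first, but the text does not say so.

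**The case against.** The strongest reply is that no investigator would read the sentence literally. A brain lesion that compresses the cord is close to a contradiction in terms, the surrounding conditions make the purpose plain, and nothing in the documents shows that anyone has enrolled a patient on the literal reading. The checklist may already carry the intended wording. All of this is fair. It makes the point a drafting error rather than a design decision, and it makes wrongful entry less likely. It does not make the sentence correct, and section 4.4 ties eligibility at outside institutions to the criteria as described in the protocol.

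A reader might also draw stronger conclusions that the documents do not support:

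- *That the sponsor meant to admit active brain metastases.* The rest of 3.2.5 points the other way.
- *That the fatal hemorrhage figure is the risk carried by brain metastases.* Section 2.2.2.4 does not say whether the two patients had brain metastases, so it gives no excess risk for this group.
- *That response would shift.* The table in section 2.2.2.2 shows response rates of 40% (n=10) with and 55% (n=20) without brain metastases. These come from dabrafenib alone and are too few to show a difference. The brain-metastasis cohort described there was asymptomatic and previously untreated, and the lesions shrank in every patient.
- *That early progression would distort the dose-escalation count.* Section 13.1 replaces a patient whose DLT status cannot be assessed because of rapid progression, and section 5.2 counts only events at least possibly related to study drug. A cycle 1 CNS event judged possibly related could still count as a DLT, but how often cannot be estimated from the documents.

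**Conclusion.** Criterion 3.2.5 is wrong as written. On either reading that the printed words allow, a symptomatic, untreated or unstable brain metastasis without cord compression is not excluded, and no other criterion generally excludes it. The likely cause is a missing connector.

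The consequence is possible inconsistency between sites and an eligibility rule that does not do what the rest of the item implies. Its size cannot be given, because the documents say neither how many such patients might present nor what excess risk they carry. The hemorrhage report is a reason for clarity, not a measure of harm. No sample size, DLT definition, escalation rule or analysis is affected.

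The conclusion rests on the wording of sections 3.1, 3.2, 4 and 10. It assumes that the unseen checklist does not already resolve the ambiguity. If it does, the protocol text still needs to agree with it.

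**What to change.** In the next amendment the sponsor should:

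1. Restate 3.2.5 so that leptomeningeal metastases, brain metastases and metastases causing spinal cord compression are named separately, and say which of the listed conditions (symptoms, lack of treatment, instability, corticosteroid need) applies to each. The documents do not settle, for example, whether treated and stable leptomeningeal disease may enter, so this is for the sponsor to decide and state.
2. Reconcile the corticosteroid exclusion with the stable-dose allowance, making clear whether the second is an exception to the first.
3. State what a positive baseline brain CT/MRI means for eligibility, and cross-refer between 3.2.5 and the calendar footnote.
4. Check that the eligibility checklist, and any equivalent used by outside institutions, carries the same wording.

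The cost is a few sentences of protocol text and a checklist review. Nothing in the statistical section needs to change.
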